8.1.2. IPSS Improvement Levels

Symptom improvement is assessed using IPSS continuous data changes as the primary efficacy endpoint and using categorical changes as a secondary efficacy endpoint. Improvement is a post-baseline score which is lower than the baseline score. Worsening is a post-baseline score which is higher than the baseline score. The number and percentage of subjects with IPSS percentage change from baseline categories of 1) improvement, 2) no change, and 3) worsening will be summarized by treatment group using both the LOCF and At Visit approaches at each scheduled post-baseline assessment.

IPSS change from baseline will be presented using five improvement levels: ≥ 1 point through ≥ 5 points. IPSS percentage change from baseline will be presented using seven improvement levels: $>0\%$, $\geq 10\%$, $\geq 20\%$, $\geq 25\%$, $\geq 30\%$, $\geq 40\%$, and $\geq 50\%$. Treatment comparisons for combination versus tamsulosin will be performed for each ≥ 2 points, ≥ 3 points, and $\geq 25\%$ using a Mantel-Haenszel test controlling for cluster at alpha=0.05.

8.1.3. Prostate Volume

Prostate dimensions are measured at the second screening visit (1b) and at each Month 12 and Month 24 (or end of treatment) visits. For analysis and reporting,

- Prostate Volume =
 $\pi/6$ (Anteroposterior Width x Cephalocaudal Width x Transverse Width).

Prostate volume percentage change from baseline is a secondary efficacy endpoint.

[Table 4](#) provides an overview of the planned prostate volume summaries and analyses. A list of planned data displays is in [Appendix 15](#): List of Data Displays. Baseline, change from baseline, and percentage change from baseline are defined in [Appendix 6](#). Last observation carried forward (LOCF) and At Visit approaches are defined in [Appendix 7](#). Summaries and analyses will be in terms of the ITT population; LOCF approach will be considered primary. Prostate volume summary statistics will be presented for baseline, Month 12 visit, and the Month 24 visit; change from baseline and percentage change from baseline summary statistics will be presented for the Month 12 and Month 24 visits.

Combination treatment and tamsulosin treatment will be compared in terms of prostate volume percentage change from baseline at the Month 12 and Month 24 visits using t-tests from the following general linear model; two-sided tests at 0.05 level of significance will be conducted:

- $\log(\text{post baseline prostate volume} / \text{baseline prostate volume}) = \log(\text{baseline prostate volume}) + \text{treatment} + \text{cluster}$

The adjusted mean estimates (mean and standard error), the adjusted mean difference, and the 95% confidence interval in terms of percentage change from baseline will be reported. The adjusted mean differences will be in terms of combination treatment minus tamsulosin treatment. The model results will be presented on same tabular summary as the arithmetic mean, standard deviation, median, minimum and maximum. The results will be presented by treatment for each scheduled post-baseline assessment.

Prostate volume adjusted mean percentage change from baseline will be plotted by treatment for each post-baseline scheduled visit in terms of each LOCF and At Visit approach.

The number and percentage of subjects with prostate volume percentage change from baseline categories of 1) improvement, 2) no change, and 3) worsening will be summarized by treatment group using both the LOCF and At Visit approaches at each scheduled post-baseline assessment. Improvement is a post-baseline prostate volume which is lower than the baseline prostate volume. Worsening is a post-baseline prostate volume which is higher than the baseline prostate volume.

Prostate volume percentage change from baseline will be presented using seven improvement levels: $>0\%$, $\geq 10\%$, $\geq 20\%$, $\geq 25\%$, $\geq 30\%$, $\geq 40\%$, and $\geq 50\%$. Treatment comparisons for combination versus tamsulosin will be performed for $\geq 25\%$ prostate volume improvement using a Mantel-Haenszel test controlling for cluster at alpha=0.05.

Supportive subgroup summaries of prostate volume percentage change from baseline will be presented in manner similar to that described for primary efficacy in Appendix 10, Examination of Covariates. Reference [Appendix 15](#) for a list of planned prostate volume subgroup tables.

Model checking associated with prostate volume percentage change from baseline will be conducted in manner similar to that described for primary efficacy in [Appendix 12](#). Reference [Appendix 15](#) for a list of prostate volume model checking outputs.

Reference [Appendix 11](#) for multiplicity considerations.

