8.1.4. Maximum Urine Flow (Qmax)

Qmax and associated total voided volume are measured at screening (Visit 1a with possible repeat at Visit 1b), baseline, and at each Month 6, Month 12, Month 18, and Month 24 (or end of treatment) visits. Qmax change from baseline is a secondary efficacy endpoint. Qmax measurements with voided volumes <125 ml will not be included in the analysis.

[Table 4](#) provides an overview of the planned Qmax summaries and analyses. A list of planned data displays is in [Appendix 15](#): List of Data Displays. Baseline, change from baseline, and percentage change from baseline are defined in [Appendix 6](#). Last observation carried forward (LOCF) and At Visit approaches are defined in [Appendix 7](#). Summaries and analyses will be in terms of the ITT population; LOCF approach will be considered primary. Qmax summary statistics will be presented for each scheduled visit; change from baseline and percentage change from baseline will be presented for each scheduled post-baseline visit.

Change from baseline Qmax at each scheduled post-baseline assessment will be compared in terms of combination treatment versus tamsulosin treatment using t-tests from a general linear model (GLM) with effects for treatment, cluster, and baseline Qmax. Two-sided tests at 0.05 level of significance will be conducted.

The adjusted mean estimates (mean and standard error), the adjusted mean difference, and the 95% confidence interval in terms of the adjusted mean difference will be presented. The adjusted mean difference will be in terms of combination treatment minus tamsulosin treatment. The model results will be presented on same tabular summary as the arithmetic mean, standard deviation, median, minimum and maximum. The results will be presented by treatment for each scheduled post-baseline assessment.

Qmax adjusted mean change from baseline will be plotted by treatment for each post-baseline scheduled visit in terms of each LOCF and At Visit approach.

Qmax improvement is also assessed using categorical changes. Improvement is a post-baseline Qmax which is higher than the baseline Qmax. Worsening is a post-baseline Qmax which is lower than the baseline Qmax. The number and percentage of subjects with Qmax percentage change from baseline categories of 1) improvement, 2) no change, and 3) worsening will be summarized by treatment group using both the LOCF and At Visit approaches at each scheduled post-baseline assessment.

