8.1.5. AUR or BPH-Related Surgical Intervention

All AUR and BPH-related surgery events during participation in the study are recorded. Subjects who discontinue from the study are followed for AUR and BPH-related surgery until the 24 month anniversary of randomization. This follow-up is in terms of biannual telephone contacts beginning at the first six month scheduled interval after discontinuation. Analyses will be in terms of events recorded at clinic visits and also collected in the biannual telephone contacts. [Table 4](#) provides an overview of the planned summaries and analyses. A list of planned data displays is in [Appendix 15](#): List of Data Displays.

Time to first AUR or BPH-related surgery will be defined as the number of days from treatment start date to date of the first event (earliest occurring of either AUR or BPH-related surgery) for each subject. Time to first AUR or BPH-related surgery is classified as a secondary efficacy endpoint and will be analyzed in terms of the Intent-to-Treat population.

Censoring will occur at the earliest of the following dates as applicable: the date of prostatectomy, the date of last contact for AUR and surgical intervention, and the date of death. For censoring, 'prostatectomy' will be determined from the eCRF prostatic surgical intervention log using the following codes associated with 'prostatectomy': open, retropubic with or without nerve-sparing, suprapubic, transvesical, perineal, salvage, laparoscopic, laparoscopic assisted. Note this excludes 'partial prostatectomy'.

The 'date of last contact for AUR and surgical intervention assessment' will be assigned as the latest of:

- Date of last treatment-phase visit
- and
- Date of last successful biannual follow-up telephone contact.

Partial dates will be handled as described in Appendix 7, Premature Withdrawals & Handling of Missing Data.

The number of subjects having the first AUR or BPH-related surgery event on or after treatment start will be tabulated by treatment, by the two annual time periods (Month 12 and Month 24), as well as by three month intervals (quarterly) along with the number of subjects at risk during each of these time periods.

Note: Cut-off dates are defined in [Appendix 6](#); definition is repeated here:

Month k Cut-off Date (for k= 3, 6, 9, 12, 15, 18, 21, 24): The maximum of [Month k clinic visit date, Month k lab visit date, Baseline Date + (k * 91/3)].

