Hospitalization details for the initial AUR will be summarized by treatment group for patient admission status (inpatient or outpatient). For inpatients, the ward type and hospitalization days will be summarized by treatment.

The frequency and percentage of subjects with multiple AUR or BPH-related surgery events will be summarized by treatment. The frequencies of subjects with 2 events, 3 events, or ≥ 4 events will be summarized. Among subjects with both events, the pattern of occurrence (AUR/Surgery or Surgery/AUR) will be summarized.

The above described summaries and analyses of AUR or BPH-related surgery will be repeated, when applicable, for the individual components 1) AUR and 2) BPH-related surgery.

All AUR and surgical intervention data will be listed by treatment and subject. Time to first AUR or BPH-related event will be listed for each subject along with the dates used in the computation of these values.

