11.7. Appendix 7: Premature Withdrawals & Handling of Missing Data

11.7.1. Premature Withdrawals

Element	Reporting Detail
General	
 Subject study completion (i.e. as specified in the protocol) is defined as completion of the 4-week placebo run-in and the 104-week study treatment period. Withdrawn subjects will not be replaced in the study. All available data from subjects who were withdrawn from the study will be listed and all available planned data will be included in summary tables and figures, unless otherwise specified. Number and percent of ITT population completing the study and those withdrawing from the study, along with eCRF recorded reasons for premature withdrawals, will be summarized by treatment and overall.
Note	This section addresses Premature Withdrawals from the study. Premature discontinuation of investigational product, along with reasons, is a separate data collection and is reported separately.

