11.7.2.2. Handling of Missing Data for Statistical Analysis

Endpoints measured at specific visits and analyzed in terms of visit numbers include: IPSS, prostate volume, Qmax, PSA, post void residual volume, BPH Impact Index (BII), BPH-Related Health Status, and PAS-SFI. Analysis of the data collected in terms of visit numbers will be performed using two different approaches to account for missing data.

1. LOCF (Last Observation Carried Forward) analysis: This involves bringing (carrying) forward the last non-missing post-baseline assessment for subjects with missing visit data and/or for subjects who discontinued from the study.
2. At Visit analysis: Missing values at post-baseline assessments are not replaced and are regarded as missing.

The LOCF approach will be considered primary for those endpoints in which both LOCF and At Visit are used. If the LOCF and At Visit results are not consistent with regard to the statistical analyses and conclusions, then further data analyses will be undertaken.

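### IPSS, Qmax and prostate-volume values taken after BPH surgery enter the efficacy analyses unchanged, so a surgical failure who is assessed afterwards can count as a responder

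*SAP*

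**What the plan says.** The three improvement definitions depend only on the direction of change from baseline.

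- IPSS (SAP 8.1.2): "Improvement is a post-baseline score which is lower than the baseline score".
- Prostate volume (SAP 8.1.3): "Improvement is a post-baseline prostate volume which is lower than the baseline prostate volume".
- Qmax (SAP 8.1.4): "Improvement is a post-baseline Qmax which is higher than the baseline Qmax".

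The treatment arms are then compared at alpha 0.05, by a Mantel-Haenszel test controlling for cluster, on IPSS falls of at least 2 points, at least 3 points and at least 25%; on a volume reduction of at least 25%; and on Qmax gains of at least 3 ml/sec and at least 30%.

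The data-handling rules favour inclusion. For withdrawn subjects, Section 11.7.1 says "all available planned data will be included in summary tables and figures, unless otherwise specified". The primary LOCF approach is described in Section 11.7.2.2: "This involves bringing (carrying) forward the last non-missing post-baseline assessment for subjects with missing visit data and/or for subjects who discontinued from the study". One measurement-level exclusion is written for these endpoints, in Section 8.1.4: "Qmax measurements with voided volumes <125 ml will not be included in the analysis".

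Prostatectomy changes how data are handled only in the time-to-event analysis of Section 8.1.5: "Censoring will occur at the earliest of the following dates as applicable: the date of prostatectomy, the date of last contact", or at death.

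**The concern.** BPH-related surgery is one of the trial's failure outcomes (SAP 2.2 and 8.1.5). Tissue removed at operation says nothing about shrinkage caused by a drug, and relief after an operation is not a response to tamsulosin or to the combination. A value recorded after surgery is nonetheless treated as any other value in the improvement-level comparisons, the general linear models (LOCF and At Visit) and the mixed model. The same man can then be a failure in one secondary endpoint and a responder in others, and under Appendix 11 the secondary endpoints can be declared formally significant once the primary succeeds.

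If surgery is commoner on tamsulosin, more control-arm men gain a favourable value they owe to surgery, and the estimated benefit of adding dutasteride is diluted.

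**Working it through.** **Search for a rule.** The SAP gives no surgery rate, sample size, standard deviation or effect size, so it has no figure of its own to reproduce. The check is whether any rule on these data mentions surgery.

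| SAP location | Rule | Condition on surgery? |
|---|---|---|
| 8.1.2, 8.1.3, 8.1.4 | Improvement is relative to baseline | No |
| 8.1.4 | Qmax dropped if voided volume is below 125 ml | No |
| Appendix 2, note i | End-of-treatment assessments also done when treatment is discontinued | No |
| Appendix 3 | Withdrawal-visit data may fill a scheduled visit within 30 days | No |
| 11.7.1, 11.7.2.2 | Available data included; LOCF carries the last value | No |
| Appendix 13 | MMRM uses scheduled post-baseline assessments | No |
| 8.1.5 | Censoring at prostatectomy | Yes, for time to event only |
| 4, 4.1.3 | Per-Protocol items 18 (prohibited non-drug therapies) or 19 (other conditions) might remove an operated man | Possibly |

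The last row gives little protection. The Per-Protocol analysis covers the primary endpoint only, is run only if that population is 80% or less of ITT, and removes whole subjects. It does not reach the Qmax, volume or responder analyses.

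**Routes by which a post-surgery value counts.** A man who stays on scheduled visits after surgery contributes post-surgery values to the LOCF, At Visit and MMRM analyses. A man who leaves contributes one only if his last assessment follows the operation. That value enters a scheduled visit only within the 30-day rule and otherwise reaches Month 24 only through LOCF.

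**Illustrative size.** Every input here is an assumption. Let pT and pC be the shares of men with a post-surgery value on tamsulosin and combination, D the extra IPSS fall after surgery, and s the share of these men turned from non-responder to responder, taken as equal in both arms.

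- Shift in mean IPSS difference = (pT − pC) × D
- Shrinkage of a responder difference = (pT − pC) × s

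| pT vs pC | IPSS shift, D = 4 / 8 / 12 | Responder shrinkage, s = 0.5 / 1.0 |
|---|---|---|
| 1% vs 0% | 0.04 / 0.08 / 0.12 | 0.5 / 1.0 points |
| 2% vs 1% | 0.04 / 0.08 / 0.12 | 0.5 / 1.0 points |
| 3% vs 1% | 0.08 / 0.16 / 0.24 | 1.0 / 2.0 points |
| 5% vs 2% | 0.12 / 0.24 / 0.36 | 1.5 / 3.0 points |
| 5% vs 1% | 0.16 / 0.32 / 0.48 | 2.0 / 4.0 points |

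For the volume cut of at least 25%, assume true rates of 10% on tamsulosin and 55% on combination (difference 45 points), with every operated man counted as a responder. At 3% vs 1% the tamsulosin rate becomes 0.10 + 0.03 × 0.90 = 0.127 and the combination rate 0.55 + 0.01 × 0.45 = 0.5545, a difference of 42.75 points. At 1% vs 0% it is 44.1 points, and at 5% vs 1% it is 40.95. The relative loss runs from 2% (0.9/45) to 9% (4.05/45).

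**The case against.** The strongest objection is that a man becomes a responder through surgery only if he is assessed in clinic afterwards, and the SAP does not show that this happens. Whether surgery leads to stopping treatment or withdrawal is a protocol matter. If treatment stops before the operation, the end-of-treatment assessment predates it and LOCF carries a pre-surgery value. Section 8.1.5 does plan that "the pattern of occurrence (AUR/Surgery or Surgery/AUR) will be summarized", and a reader might infer from this that efficacy visits continue after surgery. It does not follow, because events for that section are also collected by telephone after discontinuation, which yields no Qmax or TRUS. This objection stands: frequency and size are unknown.

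Second, analysing all randomised subjects with their observed outcomes is a legitimate treatment-policy choice, and censoring at prostatectomy is a risk-set rule that binds nothing else. This stands for the mean change analyses, including the primary. It is weaker for the improvement-level comparisons, where the SAP neither states that choice nor plans a contrast to it.

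Third, the likely bias is against the sponsor's combination, so there is no inflated claim to prevent, and the volume cut of at least 25% is not among the secondary endpoints listed in Section 2.2. Both points are correct. They lower the stakes but do not make a surgical failure a drug response.

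**Conclusion.** The point holds as a gap in the analysis rules: under the SAP as written, a post-surgery IPSS, Qmax or prostate-volume value is used like any other and may be carried to Month 24. A man who fails by surgery in Section 8.1.5 can be a responder in Sections 8.1.2 to 8.1.4, provided he is assessed after the operation. No planned analysis corrects this for the Qmax, volume or responder endpoints.

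Three stronger readings are not supported. A reader might infer that every operated man counts as an improver; he does so only if a value is taken after surgery and meets the cut. A reader might infer that the gap favours the combination; if surgery is commoner on tamsulosin, it dilutes the effect. A reader might infer that the primary IPSS analysis is invalid; it is a defensible treatment-policy analysis that lacks a stated contrast.

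The illustrated sizes (0.5 to 4.0 percentage points on a responder difference, 0.04 to 0.48 points on mean IPSS) rest entirely on assumed surgery shares, with every operated man counted in those shares assessed after surgery.

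**What to change.** 1. Add to Sections 8.1.2, 8.1.3 and 8.1.4: *for the tested improvement-level comparisons, a subject with BPH-related surgery or prostatectomy on or before the visit is a non-responder.*
2. Keep the planned ITT analyses of IPSS change, Qmax change and prostate-volume percentage change. Add a pre-specified sensitivity analysis that leaves out values obtained after the first such surgery, by LOCF for all three endpoints and also by MMRM for IPSS and Qmax.
3. Leave the PSA and post-void residual summaries unchanged. They are safety measures and should keep all observed values.

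The cost is a few lines of SAP text, one surgery flag and some additional output. The surgery dates are already used for Section 8.1.5, so nothing new is collected. The downside is that a few observed values are set aside in the sensitivity analyses, which therefore address a different question from the main ones and should be labelled so. The rule should be fixed before unblinding.

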8.1.4. Maximum Urine Flow (Qmax)

Qmax and associated total voided volume are measured at screening (Visit 1a with possible repeat at Visit 1b), baseline, and at each Month 6, Month 12, Month 18, and Month 24 (or end of treatment) visits. Qmax change from baseline is a secondary efficacy endpoint. Qmax measurements with voided volumes <125 ml will not be included in the analysis.

[Table 4](#) provides an overview of the planned Qmax summaries and analyses. A list of planned data displays is in [Appendix 15](#): List of Data Displays. Baseline, change from baseline, and percentage change from baseline are defined in [Appendix 6](#). Last observation carried forward (LOCF) and At Visit approaches are defined in [Appendix 7](#). Summaries and analyses will be in terms of the ITT population; LOCF approach will be considered primary. Qmax summary statistics will be presented for each scheduled visit; change from baseline and percentage change from baseline will be presented for each scheduled post-baseline visit.

Change from baseline Qmax at each scheduled post-baseline assessment will be compared in terms of combination treatment versus tamsulosin treatment using t-tests from a general linear model (GLM) with effects for treatment, cluster, and baseline Qmax. Two-sided tests at 0.05 level of significance will be conducted.

The adjusted mean estimates (mean and standard error), the adjusted mean difference, and the 95% confidence interval in terms of the adjusted mean difference will be presented. The adjusted mean difference will be in terms of combination treatment minus tamsulosin treatment. The model results will be presented on same tabular summary as the arithmetic mean, standard deviation, median, minimum and maximum. The results will be presented by treatment for each scheduled post-baseline assessment.

Qmax adjusted mean change from baseline will be plotted by treatment for each post-baseline scheduled visit in terms of each LOCF and At Visit approach.

Qmax improvement is also assessed using categorical changes. Improvement is a post-baseline Qmax which is higher than the baseline Qmax. Worsening is a post-baseline Qmax which is lower than the baseline Qmax. The number and percentage of subjects with Qmax percentage change from baseline categories of 1) improvement, 2) no change, and 3) worsening will be summarized by treatment group using both the LOCF and At Visit approaches at each scheduled post-baseline assessment.

Qmax change from baseline will be presented using six improvement levels: >0 ml/sec and ≥ 1 ml/sec through ≥ 5 ml/sec. Qmax percentage change from baseline will be presented using six improvement levels: $>0\%$, $\geq 10\%$, $\geq 20\%$, $\geq 30\%$, $\geq 40\%$, and $\geq 50\%$. Treatment comparisons for combination versus tamsulosin will be performed for each ≥ 3 ml/sec and $\geq 30\%$ using a Mantel-Haenszel test controlling for cluster at alpha=0.05.

Supportive subgroup summaries of Qmax change from baseline will be presented in manner similar to that described for primary efficacy in Appendix 10, Examination of Covariates. Reference [Appendix 15](#) for a list of planned Qmax subgroup tables.

Model checking associated with Qmax change from baseline will be conducted in manner similar to that described for primary efficacy in [Appendix 12](#). Reference Appendix 15 for a list of Qmax model checking outputs. As a supportive analysis, Qmax will be analyzed using a mixed-model repeated-measures (MMRM) analysis in a manner similar to that described for primary efficacy in [Appendix 13](#).

Reference [Appendix 11](#) for multiplicity considerations.

